9.2.2 Summary of Analyses

9.2.2.1 Immunogenicity Summaries

All the following analyses will be prepared on the Safety Set population by treatment group (BKZ 160 mg Q4W, Placebo / BKZ 160 mg Q4W), unless notified differently:

- Summary table displaying the number and percentage of study participants with ADAb sample status (positive, negative, total of positive and negative, missing) at each visit, overall ADAb status in the treatment period, and overall ADAb status including SFU as defined above. If there are $\geq 95\%$ of study participants included in the non-missing groups, the missing group will not be displayed on the table.
- The above summary table displaying the number and percentage of study participants in each of the ADAb status (positive, negative, total of positive and negative, missing) will be repeated by region. The overall ADAb Status in the Treatment Period will be presented for up to and including Weeks 16, 24, 52 and SFU.
- A summary table of the number (%) of study participants with the first occurrence of any ADAb positivity or treatment-emergent positivity during the study will be produced. This summary will include the following categories:
 - Any ADAb+: ADAb positive sample regardless of category during the treatment period

- Category 2: Pre ADA^b negative – treatment-emergent ADA^b positive
- Category 5: Pre ADA^b positive – treatment-boosted ADA^b positive

The table will summarize the number and percentage of study participants with first occurrence of any ADA^b sample, and also study participants who are either treatment-emergent ADA^b positive or treatment-boosted ADA^b positive for the first time at the specified time point in the study and will include the cumulative number and percentage of study participants with any ADA^b sample and treatment-emergent ADA^b positive results at each time point.

Treatment-emergent ADA^b in this table will be based on ADA^b category 7 (total treatment-emergent ADA^b).

In the event that $\geq 10\%$ of study participants are classified as category 5, the summaries will be further split by the following categories:

- Category 2: Pre ADA^b negative – treatment-emergent ADA^b positive
- Category 5: Pre ADA^b positive – treatment-boosted ADA^b positive
- A box-plot of the ADA^b titer by time of occurrence of ADA^b positivity will be created for BKZ 160mg Q4W group, as well as for the placebo/BKZ 160mg Q4W group. The ADA^b titer results will be presented on the log-scale. The time of occurrence is defined as the time in weeks from Baseline until the visit of interest when a sample is ADA^b positive. Study participants who don't have any positive ADA^b samples post-Baseline will be excluded from this analysis.
- A summary table displaying the number and percentage of study participants in each of the 9 ADA^b categories as defined above in Section 9.2.1.3 by treatment group.
- Figure summarizing the time to achieving any ADA^b positivity on a cumulative basis will be presented by treatment group. Similarly, figure representing the time to achieving treatment-emergent ADA^b positivity by treatment group will be plotted. Study participants will be considered to have an event at the time point at which an ADA^b result (or treatment-emergent ADA^b positivity) is first achieved. Treatment-emergent ADA^b in this plot will be based on ADA^b category 7 (total treatment-emergent ADA^b).

In the event that $\geq 10\%$ of study participants are classified as category 5, the lines will be further split by the following categories (thus the plot will include 3 lines per treatment group):

- Category 2: Pre ADA^b negative – treatment-emergent ADA^b positive
- Category 5: Pre ADA^b positive – treatment-boosted ADA^b positive

9.2.2.2 Efficacy Endpoint by ADA^b Summaries

Several figures, tables, and listings will be created:

- Figures will summarize efficacy response (ASAS40 and ASAS20 responders based on NRI) versus ADA^b titer quartiles. The x-axis will display the ADA^b titer quartiles at Week 16 (categorized as negative, Q1, Q2, Q3 and Q4) and the y-axis will display percentage of ASAS40 (or ASAS20) responders at Week 16.

The plots will therefore display the percentage of ASAS40 (or ASAS20) responders as a function of the number of study participants within each ADAb titer categories. Study participants with negative ADAb results at Week 16 will be included in the ‘negative’ category on the x-axis. This plot will include data from study participants only randomized to BKZ 160 mg Q4W.

For each efficacy endpoint (ASAS40 and ASAS20 responders), the figure will be repeated using Week 24 data and then using Week 52 data. These figures will include all study participants receiving BKZ and will be split by treatment group (BKZ 160 mg Q4W throughout, Placebo/ BKZ160 mg Q4W starting at Week 16). Thus, 2 figures per efficacy variable and time point will be presented.

- Two figures will summarize efficacy response (ASAS40 responders based on NRI) over time for each treatment group (Placebo/BKZ 160 mg QW4 (starting at Week 16) and BKZ throughout) by the ADAb-efficacy status groups defined above in Section 9.2.1.4 (3 lines per plot).

If $\geq 95\%$ of study participants are included in the non-missing groups, the missing group will not be displayed on the figure.

The first two figures will present data up to Week 24. Two similar figures will present data up to Week 52. These four figures will then be repeated for the ASAS20 endpoint. For each figure, the ADAb-efficacy status groups will be calculated based on data up to the timepoint of interest.

An additional figure for BKZ 160 mg Q4W group only will be generated for ASAS40 and ASAS20 with data up to Week 16.

The percent of study participants in each of the ADAb-efficacy status groups considered for efficacy sub-group analyses will be summarized.

- The ASAS20 and ASAS40 responder rates over time by ADAb-efficacy status groups defined above in Section 9.2.1.4 up to Week 16 will be presented in a tabular format with ASAS20 and ASAS40 results presented side by side (the analysis will be presented for BKZ 160 mg Q4W only). The analysis will be repeated by ADAb-efficacy status groups up to Week 24, up to Week 52, and up to SFU Visit and presented by treatment group (BKZ 160 mg Q4W and placebo/ BKZ 160 mg Q4W).
- Individual plots of bimekizumab concentrations, ADAb titer and ASAS40 response (based on NRI) will be created. All three endpoints will be plotted on the Y-axes by visit (x-axis) for the full treatment period, including SFU where a study participant has not progressed into the OLE. Plots should be labeled and grouped into the 7 pre-defined ADAb categories (described above in Section 9.2.1.3). For the Week 24 interim analysis, the 9 ADAb categories will be defined based on data up to Week 24.
- Spaghetti plots of ADAb titer (y-axis) will be reported on the log-scale by visit (x-axis) by treatment group, for all study participant in the following ADAb categories:
 - Category 2: Pre ADAb negative – treatment-emergent ADAb positive
 - Category 5: Pre ADAb positive – treatment-boosted ADAb positive

Plots will be presented using a semi-logarithmic scale for the ADAbs titers (ADAbs negative samples will therefore be excluded from the plot).

- All individual study participant-level ADAbs results will be listed including the screening assay, confirmatory assay, ADAbs sample status and titers if applicable. Note, that titer results will only be available if the confirmatory assay is positive. The listing will also include flags and reasons for exclusion for ADAbs measurements that were excluded from the by-visit summaries, as well as information on whether the BKZ concentration exceed the ADAbs assay drug tolerance limit.
- Finally, if more than 10% of the ADAbs results have been excluded from the table summaries, the ADAbs excluded results will be listed in the same listing as the one mentioned in Section 9.1.4 for excluded PK results.

9.2.3 Neutralizing anti-bimekizumab antibodies

NAb will be assessed using IL-17AA- and IL-17FF-specific assay methods, respectively. NAb results will be positive or negative to each specific NAb assay or both.

Any NAb results derived from samples with drug concentrations higher than the drug tolerance limits of the NAb assays (100 μ g/mL) will be labeled 'inconclusive'. All inconclusive results will be regarded as missing.

Participants will be assigned an overall NAb classification, inclusive of Baseline and post-Baseline results from NAb assay:

- NAb negative: No NAb positive samples for IL-17AA and IL-17FF at Baseline or post-Baseline. This group will also include study participants who have only 1 missing sample and all other available samples during the period of interest are negative. Study participants who are NAb negative will be further classified as follows:
 - ADAbs positive / NAb negative: ADAbs positive study participants who are 1) NAb negative for all available ADAbs positive samples or 2) with only one missing NAb sample and all other evaluated ADAbs positive samples are NAb negative.
 - ADAbs negative: if the study participant has all the samples as ADAbs negative or only one missing/inconclusive sample with all other available samples as negative ADAbs. Note that ADAbs negative samples are not participants to the neutralizing assay.
- NAb positive: One or more positive samples (IL-17AA positive, IL-17FF positive, or both) at Baseline or post-Baseline (regardless of missing samples) Study participants who are NAb positive will be further classified as follows:
 - Positive for IL-17AA only: one or more positive samples for IL-17AA at Baseline or post-Baseline. No positive samples for IL-17FF
 - Positive for IL-17FF only: one or more positive samples for IL-17 FF at Baseline or post-Baseline. No positive samples for IL-17AA
 - Positive for both IL-17AA and IL-17FF: one or more positive samples for both IL-17AA and IL-17FF at Baseline or post-Baseline

Drug tolerance limit for both the IL-17AA-specific NAb method and the IL-17FF-specific NAb method is 100 μ g/mL.

- NAb Missing: more than one relevant NAb samples are missing/inconclusive and other available NAb samples during the period of interest are negative, eg, missing or insufficient sample left for NAb testing.

Summary tables and a data listing will be produced to summarize the NAb status overall in the study.

The listing will be sorted by treatment group, participant identifier, and visit and, will summarize the following information for each participant assessed for NAbs:

- Visit
- Study week since first bimekizumab dose
- laboratory sampling date and time
- Time since previous dose (weeks)
- The corresponding bimekizumab plasma concentration level at each visit (ug/mL)
- Anti-bimekizumab anti-body titer at each visit
- IL-17AA NAb status and corresponding IL-17AA signal/negative control result
- IL-17FF NAb status and corresponding IL-17FF signal/negative control result

The table will provide the following overall summary statistics by treatment group (based on the total number of participants):

- The number and percentage of participants confirmed as anti-bimekizumab antibody positive and anti-bimekizumab antibody negative at any visit.
- Number and percentage of participants who are NAb positive, NAb negative and missing at any visit.

The NAb summary table will be repeated with percentages calculated on a denominator based on the number of ADA⁺ positive participants at any visit in the study.

The table summaries will display the overall NAb categories derived based on data from Baseline up to Weeks 16, 24, 52 and SFU by dose group (BKZ 160 mg Q4W and placebo / BKZ 160 mg Q4W).

For the analysis of NAb effect on pharmacokinetics, efficacy and safety of bimekizumab, the data from AS0011 may be pooled with other phase 3 studies for an integrated analysis and may be reported elsewhere.

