9.1.1 Definition of ADAb Sample Status (positive, negative, missing)

ADAb sample results will be provided as “Positive Screen” (PS) or “Negative Screen” (NS). For samples presenting anti-BKZ antibody levels that are PS, further confirmatory assay will be performed, and the result of which will be reported as either “Positive Immunodepletion” (PI) or “Negative Immunodepletion” (NI).

ADAb status for each sample will be derived as following:

- Sample values that are either NS, or PS and NI and where the BKZ concentration is less than the validated ADAb assay drug tolerance limit (200 µg/mL) will be defined as ADAb negative.
- Sample values that are either NS, or PS and NI and where the BKZ concentration exceeds the validated ADAb assay drug tolerance limit will be defined as inconclusive.
- Sample values that are PS and PI will be defined as ADAb positive (regardless of availability of a titer value).
- Missing or non-evaluable samples will be defined as missing.

PI samples will be titrated, and the ADAb titer (reciprocal dilution factor including MRD) reported. The PI samples will also be subject to a neutralizing assay to evaluate whether the anti-BKZ antibody neutralizes target binding of bimekizumab (IL17AA or IL17FF or both) in-vitro (as described in the next section).

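### A participant whose only ADAb-positive sample has no NAb result is classed ADAb positive / NAb negative, so an untested participant can be counted as negative

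*SAP*

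**What the plan says.** SAP Section 9.2.3 gives each participant one overall NAb class from Baseline and later results. The negative class begins with "NAb negative: No NAb positive samples for IL-17AA and IL-17FF at Baseline or post-Baseline" and then adds a tolerance: "This group will also include study participants who have only 1 missing sample and all other available samples during the period of interest are negative". Its ADAb-positive subclass repeats the tolerance, for participants "with only one missing NAb sample and all other evaluated ADAbs positive samples are NAb negative". The missing class applies when "more than one relevant NAb samples are missing/inconclusive and other available NAb samples during the period of interest are negative". The section also limits what is tested: "Note that ADAbs negative samples are not participants to the neutralizing assay". Section 9.1.1 agrees, since only confirmed positive samples go on to neutralization testing.

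On drug tolerance, Section 9.2.3 takes "Any NAb results derived from samples with drug concentrations higher than the drug tolerance limits of the NAb assays" (100 µg/mL), labels them inconclusive, and treats every inconclusive result as missing. The binding-assay rule in Section 9.1.1 differs: "Sample values that are PS and PI will be defined as" ADAb positive, with no condition on drug concentration. Only non-positive results above that assay's own limit (200 µg/mL) become inconclusive.

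The NAb table shows positive, negative and missing up to Weeks 16, 24, 52 and SFU. Percentages are taken over all participants, and in a repeat table over ADAb-positive participants.

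**The concern.** Allowing one missing sample is reasonable where a participant has many. Binding-antibody status rests on Baseline and eight visits through Week 52 (Section 2.2.4), so one gap leaves most of the evidence in place. For NAb, the relevant samples are only the ADAb-positive ones, and there may be just one. Section 9.2.1.4 itself provides for participants with a single positive sample. In such a participant the allowance covers all of the NAb evidence.

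At stake is the reported NAb-negative share among ADAb-positive participants, and whether a reader can see how many of them were never successfully tested. Section 9.2.3 adds that these data may be pooled with other phase 3 studies to study NAb effects on pharmacokinetics, efficacy and safety. If the classes were carried over, untested participants would sit in the comparison group.

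**Working it through.** The SAP states no NAb frequency, so there is no figure to reproduce. The check applies the Section 9.2.3 rules to possible result patterns and then sizes the effect under stated assumptions.

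**Step 1: the sole-sample case.** There is one ADAb-positive sample and its NAb result is missing.
- Positive: not met, since there is no positive result.
- Missing: not met. The count is 1 and the rule needs more than 1.
- Negative: met. There is no positive sample, one sample is missing, and the condition on all other samples holds because there are none.

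**Step 2: other patterns.** The third column requires at least one evaluable result before a participant is called negative. The fourth also keeps positives above 100 µg/mL.

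| NAb results of the ADAb-positive samples | As written | One evaluable result required | Positives also kept |
|---|---|---|---|
| one: missing | negative | missing | missing |
| one: negative, above 100 | negative | missing | missing |
| one: positive, above 100 | negative | missing | positive |
| two: missing; negative | negative | negative | negative |
| two: positive above 100; negative | negative | negative | positive |
| two: both missing | missing | missing | missing |
| two: positive above 100; positive at or below 100 | positive | positive | positive |
| two: both positive, above 100 | missing | missing | positive |

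**Step 3: size of the main point.** All inputs are assumptions. Take 100 ADAb-positive participants, 30 of them with a single ADAb-positive sample. Let 40% be truly NAb positive, and let a share m of the single samples have no NAb result. Everyone else is fully tested and no sample exceeds 100 µg/mL.
- Positive = 70 × 0.4 + 30 × (1 − m) × 0.4
- Negative as written = 70 × 0.6 + 30 × (1 − m) × 0.6 + 30 × m
- After the fix, the last term (30 × m) moves to missing.

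| m | Positive, before and after | Negative as written | Negative after | Missing after |
|---|---|---|---|---|
| 0% | 40.0 | 60.0 | 60.0 | 0.0 |
| 5% | 28 + 11.4 = 39.4 | 42 + 17.1 + 1.5 = 60.6 | 59.1 | 1.5 |
| 10% | 28 + 10.8 = 38.8 | 42 + 16.2 + 3.0 = 61.2 | 58.2 | 3.0 |

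The positive column is the same under both rules. It falls below 40 because untested participants stay in the denominator. Over evaluable participants it would be 38.8 / 97 = 40.0%.

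**Step 4: size of the secondary point.** With m = 10%, assume also that 10% of the single-sample positives lie above 100 µg/mL. Reported positives are 28 + 10.8 × 0.9 = 37.7%, against 38.8% if they are kept. If no positive sample exceeds the limit, the difference is zero.

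**The case against.** The strongest reply is that Section 9.2.3 does not name the sole-sample case. Its wording about the other samples suggests that at least one exists, and its examples for NAb Missing include too little sample for testing. On that view the case is overlooked rather than assigned to negative. It is true that the case is not named. But the missing class still needs more than one, so the literal rules leave only negative; a reading that rejects it leaves the participant with no class.

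A second reply is that one tolerated gap is the SAP's general convention (Sections 9.1.2, 9.2.1.2 to 9.2.1.4). That holds, but those rules count every scheduled sample, so they do not carry over to a count that may be one.

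A reader might infer that this rule understates NAb-positive frequency. The documents do not support that. Both denominators include everyone regardless of NAb evaluability, so moving a participant from negative to missing leaves the positive percentage unchanged.

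A reader might also infer that discarding positives above 100 µg/mL is simply an error. That too goes too far. The two assays are different methods with different limits, and whether a NAb positive above the limit is reliable is a matter for a validation report that is not at hand. The SAP gives no expected concentrations, so such samples may be few or absent.

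Finally, the NAb output is descriptive, is not planned for the Week 24 interim report, and comes with a listing of concentration and NAb status by visit. These facts limit the consequence. The listing may expose affected cases but does not correct the tables.

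**Conclusion.** The main point holds. Section 9.2.3 as written puts a participant with one ADAb-positive sample and no usable NAb result into ADAb positive / NAb negative. The reported NAb-negative share can be too high and missing data can be hidden. In the illustration the shift is 0 to 3.0 percentage points of ADAb-positive participants, resting on the assumed 30% with a single sample and 0 to 10% of those without a result. The true size cannot be determined from the SAP, and it is zero if the pattern does not occur. The primary endpoint and the testing hierarchy are untouched.

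The treatment of positives above 100 µg/mL stands only as an unexplained difference from Section 9.1.1. NAb positivity could be understated if such samples occur; the SAP does not show that it is.

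**What to change.** In Section 9.2.3, require at least one evaluable NAb result for ADAb positive / NAb negative, and class participants who have ADAb-positive samples but no evaluable NAb result as NAb Missing. The one-missing allowance can otherwise stay.

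For results above 100 µg/mL, either give the reason from the assay validation for discarding positives, or follow Section 9.1.1 and label only NAb-negative results above the limit as inconclusive.

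The cost is about two sentences and a small programming change. The missing group may grow slightly.

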10 SAFETY ANALYSES

Safety variables will be analyzed on the SS, as well as on the MS for analyses covering the Maintenance Period (MP) only.

Summaries for the MP will also include the SFU period for study participants that do not roll enter the OLE or discontinue early in the MP. The SFU period for study participants that discontinue in the DBTP will only be summarized in the Overall Period tables.

10.1 Extent of exposure

Two summary tables will be created to describe the extent of exposure.

The first table consists of a descriptive summary of study medication duration (in days), total study medication duration in (subject-years), and total time at risk (in subject-years). The information will be presented overall (ie, for the entire treatment period (Double-Blind Treatment Period (DBTP) and Maintenance Period (MP) combined)) as well as by treatment periods.

Study medication duration in subject-years is obtained as study medication in days divided by 365.25. Similarly, total time at risk in subject-years is obtained as total time at risk in days divided by 365.25.

A second summary will be created on the cumulative study medication duration for the overall period, as well as by treatment periods.

- The following time durations categories will be considered for the overall period: ≥ 0 weeks, ≥ 16 weeks, ≥ 24 weeks, ≥ 48 weeks.
- The following time durations categories will be considered for the Double-Blind Treatment Period: ≥ 0 weeks, ≥ 4 weeks, ≥ 8 weeks, ≥ 12 weeks.
- The following time durations categories will be considered for the Maintenance Period: ≥ 0 weeks, ≥ 16 weeks, ≥ 24 weeks, ≥ 36 weeks.

A by-study participant listing of date of first and last dose and the duration of exposure will be performed.

The study medication duration (in days) and the time at risk (in days) are defined depending on the study period of interest. See Section 10.1.1 to Section 10.1.5 for further details.

Throughout this section, date of last clinical contact for each study participant is defined as the maximum of [last visit date including SFU visit, last AE start date (including imputed AE start dates), date of study termination or completion, last date of study drug administration].

10.1.1 Duration of exposure and time at risk in the Double-Blind Treatment Period (DBTP)

- The study medication duration during the DBTP will be calculated as follows:

$$\text{Date of last dose (DBTP)} - \text{Date of first dose (DBTP)} + 28$$

(this formula also applies for study participants who discontinue/lost to follow-up during the DBTP).

- If the date of last dose of the DBTP + 28 days extends to a date beyond the date of first dose of the Maintenance period, then this calculation reverts to:

$$\text{Date of first dose (MP)} - \text{Date of first dose (DBTP)} + 1$$

Note: If the date of last dose + 28 extends to a date beyond the final visit date (not including SFU), then this calculation reverts to:

$$\text{Date of last visit (not including SFU)} - \text{Date of first dose} + 1$$

- For study participants who die during the DBTP, this calculation reverts to:

$$\text{Date of death} - \text{Date of first dose (DBTP)} + 1$$

- The time at risk during the DBTP will be calculated as follows:

- For study participants who complete the final visit of the DBTP and continue to the Maintenance Period:

$$\text{Date of first dose (MP)} - \text{Date of first dose (DBTP)} + 1$$

- For study participants who discontinue on or prior to the final visit of the DBTP (ie, Week 16), use the minimum of the following:

- Total number of days in the DBTP:

- For those that discontinue prior to the Week 16 visit, use 112 days,
 - For those that discontinue at the Week 16 visit, use the total number of days based on Week 16 visit date, which can be a maximum of 115 days due to visit windows

- $$\text{Date of last clinical contact} - \text{Date of first dose (DBTP)} + 1$$
, last clinical contact can be defined as last scheduled site visit.

- For study participants who die during the DBTP, then this calculation reverts to:

$$\text{Date of death} - \text{Date of first dose (DBTP)} + 1$$

